2.1.2 Primary endpoint(s)

PART 1:

The primary endpoint is the number of patients with DLTs within the first cycle of treatment, which will be assessed for dose escalation in order to meet the objective of determination of the MTD of the combination BI 836880 and ezabenlimab in patients with locally advanced or metastatic non-squamous NSCLC.

PART 2:

The primary endpoint is Objective Response (OR) defined as best overall response (RECIST 1.1) of complete response (CR) or partial response (PR) from first treatment infusion until the earliest of disease progression, death or last evaluable tumour assessment before start of subsequent anti-cancer therapy, lost to follow-up, or withdrawal of consent. In case of recurrent glioblastoma (GBM), assessment will be based on RANO (Response Assessment in Neuro-Oncology) criteria.

[figure not shown]

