5.2.3 Safety laboratory parameters

Blood and urine samples for assessment of general safety laboratory examinations have to be collected at the time points specified in the [Flow Chart](#), but should be more frequent in case of relevant findings, e.g. in case of grade 4 neutropenia, as any non-proven recovery within 7 days will be counted as DLT or proteinurea, for which determination of CTCAE grade 2 vs. grade 3 need to be done by quantitative measurement. Laboratory values planned for V1D1 (=day of administration) must be available before start of infusion in order to evaluate eligibility of patient to receive treatment. Therefore it's possible to take blood sample a valuable time ahead (usually the day before treatment but possible up to approximately 72 hours before). Safety laboratory examinations will include hematology, biochemistry, coagulation and urine analysis:

Hematology	Hemoglobin, white blood cell count (WBC) with differential, platelets (PLT)
Biochemistry inorganic	Glucose, sodium, potassium, calcium, magnesium, phosphate, creatinine, AST, ALT, alkaline phosphatase (AP), lactate dehydrogenase (LDH), bilirubin, serum urea nitrogen (or urea), thyroid panel [TSH, free T4, and free T3]], total protein, albumin, uric acid, CK, In case of pathological CK elevated, then CK-MB, additional troponin, and myoglobin as available should be reactively tested and the findings documented. Serum immunoglobulin levels (IgG, IgM, IgA; IgE) and direct antiglobulin test have to be measured at Screening and at occurrence of infusion related reactions.
Coagulation	Activated partial thromboplastin time (aPTT), prothrombin time (PT) or international normalised ratio (INR) where indicated (e.g. treatment with vitamin K antagonists)
Urine	pH, glucose, erythrocytes, leukocytes, protein, nitrite will be analyzed primarily qualitatively by dipstick. In case of clinically relevant findings, further evaluation should be performed and the findings documented. A positive urine dipstick for protein of $\geq 2+$ (CTCAE gr 2) has to be followed by a determination of the ratio of urine protein to creatinine (UPCR) in a morning spot urine sample. In case of a ratio ≥ 0.5 , a 24 hour urine collection for protein loss has to be performed. The 24 hour urine collection will be repeated every time the UPCR ratio is ≥ 0.5 as often as clinically indicated.

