5.2.6 Other safety parameters

5.2.6.1 Dose limiting toxicities (DLTs)

The occurrence of any of the toxicities presented in Table 5.2.6.1: 1 will be considered a DLT, if assessed by the investigator to be related to the administration of either of the study drugs. All DLTs occurring during Part 1 of the study will be considered an AESI and reported on the SAE form. Once the dose escalation part of the study has been completed (Part 1), DLTs no longer need to be reported (i.e. Part 2).

Incidence and severity of adverse events will be graded according to the common terminology criteria for adverse events (CTCAE, version 5.0).

Table 5.2.6.1: 1 Dose Limiting Toxicities (according to CTCAE V5.0)

Drug related toxicity category	Criteria defining a DLT*
Hematologic	
• Grade 4 neutropenia ($<500/\text{mm}^3$) lasting ≥ 5 days or complicated by infection• Grade ≥ 3 documented infection with neutropenia.• Grade ≥ 3 febrile neutropenia ($\text{ANC} < 1000/\text{mm}^3$ complicated by fever $\geq 38.3^\circ\text{C}$ or $101^\circ\text{F}^\circ\text{C}$ or a sustained temperature of $\geq 38.0^\circ\text{C}$ (100.4°F) for more than 1 hour.• Grade 3 thrombocytopenia ($\geq 25,000/\text{mm}^3$ and $< 50,000/\text{mm}^3$) associated with bleeding or requiring platelet transfusion.• Grade 4 thrombocytopenia ($< 25,000/\text{mm}^3$).• Grade 4 anaemia (i.e., life-threatening consequences or urgent intervention indicated).

Table 5.2.6.1: 1 Dose Limiting Toxicities (according to CTCAE V5.0) (cont'd)

Drug related toxicity category	Criteria defining a DLT*

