7.3.1 Primary endpoint analyses

7.3.1.1 Primary endpoint analyses for Part 1

In order to identify the MTD(s) and the recommended dose(s) for Part 2 of the trial, the number of patients with DLTs at each dose combination during the Part 1 MTD evaluation period (the first cycle of the BI 836880 plus ezabenlimab combination) must be presented by descriptive statistics. Patients who discontinue during the first treatment cycle for reasons other than a DLT will be excluded from the determination of the MTD. In addition, the number of patients with DLTs that occurred during the entire treatment period will be summarized at each dose level. The BLRM will be rerun to re-evaluate the MTD and RP2D together with all relevant data collected during Part 2.

7.3.1.2 Primary endpoint analyses for Part 2

The primary endpoint for Part 2 of the trial is OR defined by confirmed CR or PR according to RECIST 1.1 for all cohorts except GBM as assessed by the Investigator. OR in GBM cohort will be evaluated using RANO criteria. Overall response will be analyzed in terms of the shrinkage estimator of the OR rate (ORR) based on BHM.

Note on primary endpoint analysis in cohort F:

In addition, OR from stage I and stage II will be analyzed separately using a Bayesian approach with meta-analytic predictive (MAP) prior after completion of stage II. Please refer to [Section 7.1.2](#) for more details on the derivation of the MAP prior and the final decision criterion. A naïve estimate (observed objective response rate) along with 95% CI (Clopper-Pearson) will also be provided.

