10.6.1 Hypothetical data scenarios

These scenarios reflect potential on-study data constellations and related escalation as allowed by the model. It is assumed that each cohort has 3 patients who are all evaluable. At the 1st occurrence of a DLT, additional 3 patients will be added to the current cohort. For each scenario, the probability of overdose for the current dose, as well as the next potential dose and related probabilities of under-dosing, target dosing, and over-dosing are shown (see [Table 10.6.1: 1](#)).

For example, Scenario 1A represents the case that no DLT is observed in the first 2 patients at the starting dose combination of BI 836880 360 mg plus ezabenlimab 240 mg (denoted by 360 mg/240 mg for easier reference). In this case, there are 2 next allowed dose combinations from the model, i.e., 500 mg/240 mg, and 720 mg/240 mg, among which, 720 mg/240 mg has the highest probability of being in the target region. Scenario 1B shows 1 DLT observed in 3 patients at 360mg/240mg, the dose recommended will remain at this level. But if 3 more patients is added to this cohort and number of DLT remains at 1, the next dose allowed will be 500mg/240mg (Scenario 1C).

Scenario 2D: after no DLT observed in 2 patients of 360mg/240mg dose combination, if 2 DLT observed in 6 patients of 500mg/240mg cohort, the dose cannot be escalated further.

Scenario 3A: no DLT in first 3 cohort, the next recommended dose combination will be 1000mg/240mg. If there is 1 DLT out of 3 or 6 patients in 720mg/240mg cohort, the dose recommended will remain at 720mg/240mg as shown in Scenario 3B-3E.

Table 10.6.1: 1 Hypothetical data scenarios

Scenario	Dose comb. BI 836880/ ezabenlimab (mg/mg)	# DLT	# Pat	Current Dose: P(OD)	Next allowed dose comb. (mg/mg)*	Summary of toxicity of next Combination dose		
						P(under dose)	P(target dose)	P(over dose)
1A	360/240	0	2	0.075	500/240 720/240	0.578 0.427	0.312 0.363	0.110 0.210
1B	360/240	1	3	0.226	360/240	0.391	0.384	0.226
1C	360/240	1	6	0.080	500/240	0.461	0.406	0.133
2A	360/240 500/240	0 0	2 3	0.034	720/240	0.551	0.347	0.102
2B	360/240 500/240	0 1	2 3	0.151	500/240	0.434	0.415	0.151
2C	360/240 500/240	0 1	2 6	0.055	720/240	0.392	0.449	0.160
2D	360/240 500/240	0 2	2 6	0.188	500/240	0.313	0.499	0.188
3A	360/240 500/240 720/240	0 0 1	2 3 3	0.139	720/240	0.395	0.466	0.139
3B	360/240 500/240 720/240	0 0 1	2 3 6	0.053	720/240	0.539	0.408	0.053
3C	360/240 500/240 720/240	0 0 2	2 3 6	0.168	720/240	0.289	0.543	0.168

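### The Section 5.2.3 remark on when Grade 4 neutropenia counts as a DLT (7 days) does not match the governing DLT table in Section 5.2.6.1 (5 days or more)

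*Protocol*

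**What the plan says.** Section 5.2.3 says that safety laboratory samples should be taken more often than the flow chart requires when there are relevant findings. Its example is extra counts "in case of grade 4 neutropenia, as any non-proven recovery within 7 days will be counted as DLT".

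Section 5.2.6.1 is the formal definition: "The occurrence of any of the toxicities presented in Table 5.2.6.1: 1 will be considered a DLT", provided the investigator judges the event related to either study drug. The hematologic row of the table lists Grade 4 neutropenia "lasting ≥ 5 days or complicated by infection".

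Section 5.2.7.1, under adverse events of special interest, points to Section 5.2.6.1 for the definition of a DLT. Section 4.1.4 refers to the same table. Both durations stand in the current text.

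The DLT count is the Part 1 endpoint in Section 2.1.2: "The primary endpoint is the number of patients with DLTs within the first cycle of treatment". Section 7.3.1.1 summarises DLTs in cycle 1 and over the whole treatment period, and adds: "The BLRM will be rerun to re-evaluate the MTD and RP2D together with all relevant data collected during Part 2".

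**The concern.** Both passages say when Grade 4 neutropenia counts as a DLT, and they differ in two ways. The limits are different (7 days against 5 days). The rules also differ in kind: Section 5.2.3 counts recovery that has not been proven, while the table needs a duration or an infection.

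The place of the remark matters because Section 5.2.3 is the instruction meant to prompt extra counts. A site that takes 7 days as its target can satisfy that remark and still leave no record of whether the episode reached 5 days. A later adjudicator working from the table could not recover that information.

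The DLT count is the Part 1 primary endpoint and the binomial outcome in the BLRM (Section 7.1.1.1), so a patient counted differently enters both.

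**Working it through.** No sample size or error rate is involved. The check sets the two wordings side by side, asks what the scheduled counts can show, and reads the protocol's own tables for the effect of one patient.

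**1. Classification.** Take a related Grade 4 episode in cycle 1, and assume that recovery in Section 5.2.3 means a count no longer in the Grade 4 range (the section does not define it).

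| Episode | Table 5.2.6.1: 1 | Section 5.2.3 remark |
|---|---|---|
| Under 5 days, recovery shown, no infection | Not a DLT | Not captured |
| 5 to under 7 days, recovery shown, no infection | DLT | Not captured |
| Longer than 7 days | DLT | DLT |
| Complicated by infection, recovery shown within 7 days | DLT | Not captured |
| Recovery not documented within 7 days, 5-day duration not shown, no infection | Not shown to be a DLT | DLT by default |

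The second and fifth rows hold the conflict over duration. The fourth row shows only that the remark omits the infection criterion.

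**2. What scheduled counts can show.** The Part 1 flow chart places cycle 1 visits at days 8 and 15 after the first three days, each with a window of -1/+2 days.
- Nominal gap: 15 − 8 = 7 days.
- Shortest gap within the windows: 14 − 10 = 4 days.
- Longest gap within the windows: 17 − 7 = 10 days.

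If Grade 4 is found on day 8 and the count has recovered on day 15, recovery is shown 7 days later and the remark can be met. Those two counts do not show whether the episode lasted 5 days. Only additional counts can.

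**3. What one patient can do to the model.** Table 10.6.1: 1 gives these scenarios at 500 mg/240 mg, each after 0 DLTs in 2 patients at 360 mg/240 mg:

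| Scenario | DLTs / patients | P(overdose), current dose | Next allowed |
|---|---|---|---|
| 2A | 0/3 | 0.034 | 720/240 |
| 2B | 1/3 | 0.151 | 500/240 |
| 2C | 1/6 | 0.055 | 720/240 |
| 2D | 2/6 | 0.188 | 500/240 |

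One added DLT turns escalation into a hold in both pairs. Section 10.6.1 says of 2D: "if 2 DLT observed in 6 patients of 500mg/240mg cohort, the dose cannot be escalated further". These are hypothetical data, and Section 7.1.1.1 calls the data behind the prior illustrative, so they show sensitivity and not what happened in the trial.

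**4. How often it could arise.** Section 1.2.1 pools 359 combination patients, including this trial. Grade 4 AEs were reported in 13 (13/359 = 3.6%), each such AE in a single patient. At most one patient per reported term is therefore possible, or 1/359 = 0.3%. With BI 836880 alone at 720 mg every 3 weeks, neutropenia was one of the Grade 4 AEs reported in two patients (8.7%, so 2/0.087 ≈ 23 patients at that dose). Section 4.1.2.1 does not list neutropenia among the monotherapy DLTs. The synopsis gives 22 patients entered in Part 1.

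**The case against.** The strongest reply is that there is only one definition. Section 5.2.7.1 names Section 5.2.6.1, Section 4.1.4 refers to its table, and Section 5.2.3 gives an example within a sampling instruction. This stands. A reader might infer that the protocol carries two competing definitions of the Part 1 primary endpoint, but it has one governing definition and a remark that does not agree with it.

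Three further limits also stand.
- Section 5.2.3 states a condition that is sufficient for a DLT. It does not say that a 5- or 6-day episode is not one, so the difference is an episode left uncaptured and not one expressly excluded.
- Section 5.2.3 sets no sampling interval. It would be too strong to say that it tells sites to sample on a 7-day schedule. Sites may have sampled often enough to meet either rule.
- Scenarios 2A to 2D are hypothetical, and the SMC decided on all available safety data (Sections 3.1 and 5.2.6.3). A reader might infer that the selected dose is in doubt, but nothing in the document shows that any episode fell between the two wordings.

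The reply does not remove the mismatch. A governing table settles how a documented episode is classified. It does not supply counts that were never taken, and it does not say what to do with undocumented recovery, which only Section 5.2.3 addresses.

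**Conclusion.** The point holds as an inconsistency between a sampling remark and the governing DLT table. It affects related Grade 4 episodes without infection that last 5 to under 7 days, and episodes whose recovery was not documented.

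The practical size is small. Section 4.1.2.2 records that the SMC has selected the Part 2 dose, DLTs need not be reported in Part 2, and no more patients will be included. The pooled data make an affected episode unlikely among about 22 Part 1 patients. That inference rests on reported AE terms, so a Grade 4 laboratory value not recorded as an AE would not appear in it. The document does not state how many Part 1 patients had Grade 4 neutropenia, or for how long.

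What remains exposed is the reported Part 1 DLT count, its documentation and the BLRM rerun. That justifies a correction and a short check, but no conclusion about past dose decisions.

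**What to change.** - Reconcile Section 5.2.3 with Table 5.2.6.1: 1 so that the sampling instruction and the DLT table state the same rule, including how recovery that is not documented is treated. Which duration applies is for the sponsor to settle.
- Before the final DLT summary and the BLRM rerun in Section 7.3.1.1, list the Part 1 Grade 4 neutropenia episodes from the laboratory data as well as the AE data. Mark any that the two wordings classify differently or whose duration cannot be established.
- State in the report which rule was used to adjudicate Part 1 DLTs. If any episode is marked, give the DLT count and the BLRM result under both wordings.

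The cost is one sentence in the protocol and a check of about 22 patients. If no episode is marked, one line in the report closes the point.

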5.2.5 Echocardiography

Echocardiography have to be conducted at screening (not older than 21 days before treatment start) and at EoT-visit. During treatment phase it has only to be done when clinically indicated.

5.2.6 Other safety parameters

5.2.6.1 Dose limiting toxicities (DLTs)

The occurrence of any of the toxicities presented in Table 5.2.6.1: 1 will be considered a DLT, if assessed by the investigator to be related to the administration of either of the study drugs. All DLTs occurring during Part 1 of the study will be considered an AESI and reported on the SAE form. Once the dose escalation part of the study has been completed (Part 1), DLTs no longer need to be reported (i.e. Part 2).

Incidence and severity of adverse events will be graded according to the common terminology criteria for adverse events (CTCAE, version 5.0).

Table 5.2.6.1: 1 Dose Limiting Toxicities (according to CTCAE V5.0)

Drug related toxicity category	Criteria defining a DLT*
Hematologic	
• Grade 4 neutropenia ($<500/\text{mm}^3$) lasting ≥ 5 days or complicated by infection• Grade ≥ 3 documented infection with neutropenia.• Grade ≥ 3 febrile neutropenia ($\text{ANC} < 1000/\text{mm}^3$ complicated by fever $\geq 38.3^\circ\text{C}$ or $101^\circ\text{F}^\circ\text{C}$ or a sustained temperature of $\geq 38.0^\circ\text{C}$ (100.4°F) for more than 1 hour.• Grade 3 thrombocytopenia ($\geq 25,000/\text{mm}^3$ and $< 50,000/\text{mm}^3$) associated with bleeding or requiring platelet transfusion.• Grade 4 thrombocytopenia ($< 25,000/\text{mm}^3$).• Grade 4 anaemia (i.e., life-threatening consequences or urgent intervention indicated).

Table 5.2.6.1: 1 Dose Limiting Toxicities (according to CTCAE V5.0) (cont'd)

Drug related toxicity category	Criteria defining a DLT*
Non-hematologic	
Non-laboratory toxicity
 
 Any Grade 4 or 5 AE other than disease progression. Any Grade 2 drug-related uveitis or eye pain or blurred vision that does not respond to topical therapy and does not improve to Grade 1 severity within 2 weeks or requires systemic treatment. Any treatment-related Grade ≥ 2 toxicity that occurred during Cycle 1 that persists and results in an inability to administer ezabenlimab or BI 836880 on Cycle 2 Day 1. Grade ≥ 2 pneumonitis of any duration Any toxicity Grade ≥ 3 toxicity except: 
 Grade 3 immune-related AE that resolves to \leq Grade 1 or to baseline with immunosuppressive therapy within 2 weeks Grade 3 asymptomatic endocrine disorders (thyroid, pituitary, and/or adrenal insufficiency) that are managed with or without systemic corticosteroid therapy and/or hormone replacement therapy. Grade 3 or 4 elevation in serum amylase and/or lipase that is not associated with clinical or radiographic evidence of pancreatitis Grade 3 nausea or Grade 3 vomiting will be defined as DLT when it persists at Grade 3 longer than 48 hours despite adequate medical intervention. Alopecia Grade 3 fatigue that persists less than 7 days Grade 3 infusion related reaction which can be controlled by appropriate medication according to investigator's decision, and the subsequent infusion will not be delayed for more than two weeks. Grade 3 rash that resolves to \leq Grade 1 within 2 weeks Grade 3 endocrine disorders (thyroid, pituitary, and/or adrenal insufficiency) that are managed with or without systemic corticosteroid therapy and/or hormone replacement therapy, and the patient is asymptomatic. Grade 3 tumour flare.
	
Laboratory toxicity
 
 Hypertension: systolic blood pressure $>=160$ mm Hg or diastolic blood pressure $>=100$ mm Hg, confirmed by second measurement of an additional set of 3 BP measurements, or 3 sequential ambulatory blood pressure measurements when indicated (e.g. white coat effect), and which cannot be controlled by hypertensive medication and which requires a dose reduction / discontinuation of trial medication(s) Grade 3 proteinuria (urinary protein $>=3.5$ g/24 hrs; 4+ proteinuria) AST or ALT >3 times ULN and concurrent total bilirubin >2 times ULN without initial findings of cholestasis. \geq Grade 4 AST or ALT of any duration 
NOTE: Any laboratory abnormality which is considered not clinically relevant by the investigator or resolves spontaneously, or resolves with appropriate treatment is not a DLT. Clinically relevant abnormalities must be documented as AEs.

Re-Treatment Delay	All related AE leading to an interruption of BI 836880 or ezabenlimab for more than 14 days until recovery to baseline.

*It is the responsibility of the investigator to follow-up on the toxicities in a timely manner.

Late immune-related DLTs are irAEs that meet the same grading criteria as DLT criteria, but occur after Cycle 1 administration during Part 1. These, as well as all toxicities will be monitored throughout the trial. If any late immune-related DLT is reported during dose-escalation, the BLRM will be rerun including the late immune-related DLT, and updated

results will be reviewed in the SMC meeting to recommend the next dose level and cohort size.

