3.3.4.1 Withdrawal from trial treatment

An individual patient is to be withdrawn from trial treatment if:

- The patient wants to withdraw from trial treatment, without the need to justify the decision.
- The patient needs to take concomitant drugs that interfere with the investigational product or other trial medication.
- The patient can no longer be treated with trial medication for other medical reasons (such as surgery, adverse events, other diseases, or pregnancy).
- The patient can no longer be treated with trial drug after a drug related Adverse Event CTCAE Grade 4.
- The patient can no longer be treated with trial drug after a DLT, which did not recover to CTCAE Grade 1 or pre-treatment values within 2 weeks (not applicable for part 2)
- The patient has repeatedly shown to be non-compliant with important trial procedures and, in the opinion of both, the investigator and sponsor representative, is not willing or able to stick to the trial requirements in the future.

Given the patient’s agreement, the patient will undergo the procedures for early treatment discontinuation and follow up as outlined in the [Flow Chart](#) (FC) and [Section 6.2.3](#).

For all patients, the reason for withdrawal from trial treatment (e.g. adverse events) must be recorded in the eCRF. These data will be included in the trial database and reported.

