4. TREATMENTS

4.1 INVESTIGATIONAL TREATMENTS

4.1.1 Identity of the Investigational Medicinal Products

In this trial, the IMP BI 836880 will be switched to a new pharmaceutical formulation which is diluted in a standard 5% Glucose/Dextrose solution. The new formulation will be made available in this trial at the latest before expiry of the old formulation prepared with a drug specific Diluent. Details of the trial medications, BI 836880, ezabenlimab, and respective diluents, are presented in Tables 4.1.1: 1 and 4.1.1: 2, in the IBs for BI 836880 and ezabenlimab as well as in the Instruction for the Pharmacist (IfP).

Table 4.1.1: 1 BI 836880

Substance:	BI 836880
Pharmaceutical formulation:	Solution for infusion
Source:	Boehringer Ingelheim Pharma GmbH & Co. KG
Unit strength:	10 mg/ml (vials with 10 ml)
Posology	rate controlled infusion on Day 1 of each 3-week cycle
Route of administration:	i.v.
Duration of use:	until progression, unacceptable toxicity, or up to a maximum of 53 cycles

Table 4.1.1: 2 Ezabenlimab (BI 754091)

Substance:	Ezabenlimab (BI 754091)
Pharmaceutical formulation:	Solution for Infusion or Concentrate for solution for infusion
Source:	Boehringer Ingelheim Pharma GmbH & Co. KG
Unit strength:	20 mg /mL (15 mL vial) or 20 mg /mL (12 mL vial)
Posology	rate controlled infusion on Day 1 of each 3-week cycle
Route of administration:	i.v.
Duration of use:	until progression, unacceptable toxicity, or up to a maximum of 53 cycles

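### In Table 5.2.6.1: 1 the note on resolving laboratory abnormalities contradicts the Grade 4 AST/ALT criterion, and no text says which prevails

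*Protocol*

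**What the plan says.** Section 5.2.6.1 of the protocol opens with a general rule: a toxicity listed in Table 5.2.6.1: 1 is a DLT if the investigator judges it related to either drug. Under laboratory toxicity the table lists, at that grade or higher, "Grade 4 AST or ALT of any duration". It also lists Grade 3 proteinuria, and AST/ALT above 3 times ULN together with bilirubin above 2 times ULN.

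The note that closes the same cell reads: "Any laboratory abnormality which is considered not clinically relevant by the investigator or resolves spontaneously, or resolves with appropriate treatment is not a DLT". It adds that clinically relevant abnormalities must be documented as AEs.

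The non-laboratory block of the table contains "Any Grade 4 or 5 AE other than disease progression" and a general Grade 3-or-higher row. One exception to that row is "Grade 3 or 4 elevation in serum amylase and/or lipase that is not associated with clinical or radiographic evidence of pancreatitis".

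The DLT count is used in three places:
- Section 2.1.2 makes the number of patients with DLTs in the first cycle the Part 1 primary endpoint.
- Section 7.1.1.1 feeds that number to the BLRM.
- Section 7.3.1.1 asks for the Cycle 1 DLT count, a DLT count over the whole treatment period by dose level, and a BLRM rerun to re-evaluate the MTD and RP2D.

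**The concern.** A criterion that applies whatever the duration is meant to count transient events. A note that removes every resolving laboratory abnormality removes exactly those events. The two lines give opposite answers for the same patient: someone with a drug-related Grade 4 ALT rise that recovers.

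The not-clinically-relevant limb of the note leaves room for judgement. The two resolution limbs do not, and neither does the AST/ALT line. Two investigators who each follow the text could therefore record the same event differently. An endpoint definition should give one answer per patient, and with dose cohorts of a few patients a single DLT can matter to the model.

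**Working it through.** **Step 1: the texts side by side.** Take a drug-related AST or ALT rise of Grade 4 that later resolves.

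| Text | Reading |
|---|---|
| Opening rule, Section 5.2.6.1 | DLT, because the listed toxicity occurred |
| AST/ALT line of the table | DLT, whatever the duration |
| Note in the same cell | Not a DLT, because it resolved |
| Grade 4 or 5 row | DLT if it reaches laboratory events recorded as AEs, but it sits under the non-laboratory heading |
| Grade 3-or-higher row | Probably DLT: its exceptions name amylase and lipase but not AST/ALT, which suggests the block reaches laboratory values |
| Section 4.1.4, Part 1 re-administration text | Favours DLT: it glosses a DLT as a drug-related Grade 3 or 4 AE according to the table |

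Most of these favour counting the event. None says that it overrides the note. The table footnote and Sections 5.2.6.2, 5.2.6.3, 7.1.1.1 and 7.3.1.1 set no order either.

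**Step 2: the neighbouring criteria.** The proteinuria and AST/ALT-plus-bilirubin lines say nothing about duration, so the note qualifies them without contradicting them. It does so with no time limit, whereas the exceptions for Grade 3 immune-related events and Grade 3 rash in the same table require resolution within 2 weeks.

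**Step 3: what one patient does to the model.** The model is that of Section 7.1.1.1:
- logit(π1) = log α1 + β1·log(d1/720) and logit(π2) = log α2 + β2·log(d2/240)
- π0 = π1 + π2 − π1·π2
- odds(π) = odds(π0)·exp(η·(d1/720)·(d2/240))

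The mixture priors come from Table 7.1.1.1: 3, with η normal, mean 0, SD 0.707. Prior draws (2 to 4 million per run) are weighted by the product of π^r·(1−π)^(n−r) over doses. The overdose probability is the weighted share of draws with π ≥ 0.33, and a dose is permitted if this is below 0.25. Repeat runs agree to about 0.001.

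Reproducing Table 10.6.1: 1 first (overdose probability):

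| Scenario | Dose | Printed | Recomputed |
|---|---|---|---|
| 1A | 720/240 | 0.210 | 0.210 |
| 1B | 360/240 | 0.226 | 0.224 |
| 1C | 500/240 | 0.133 | 0.132 |
| 2B | 500/240 | 0.151 | 0.151 |
| 2D | 500/240 | 0.188 | 0.184 |
| 3C | 720/240 | 0.168 | 0.171 |
| 3D | 720/240 | 0.222 | 0.221 |

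Now move one patient. With 0/2 at 360/240 and 0/3 at 500/240, the overdose probability at 720/240 is:
- 3/6: 0.374, fails
- 2/6 (one DLT not counted): 0.171, passes
- 2/5 (that patient also leaves the MTD set): 0.221, passes
- 1/6: 0.055, passes, so moving from 2/6 to 1/6 changes no decision

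At the starting dose:
- 1/3 gives 0.224 at 360/240, 0.295 at 500/240 and 0.416 at 720/240, so the dose stays at 360/240.
- 0/3 gives 0.050, 0.081 and 0.174, so 500/240 and 720/240 are both open.

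The 2/5 case is the less usual one. Both drugs are given as a "rate controlled infusion on Day 1 of each 3-week cycle", so a patient observed for 3 weeks stays evaluable. The patient drops out only if the withdrawal in Section 3.3.4.1 ("The patient can no longer be treated with trial drug after a drug related Adverse Event CTCAE Grade 4") is dated within Cycle 1 and the event is not called a DLT.

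**The case against.** A sensible reading exists. A specific line on duration is not normally emptied by a general note, and the texts in Step 1 point the same way. A clinically relevant Grade 4 rise must be recorded as an AE, which brings it within the wording of the Grade 4 or 5 row. The separate re-treatment-delay row makes a DLT of a related AE that interrupts treatment for more than 14 days, and a drug-related Grade 4 event ends treatment altogether, although whether a permanent stop is an interruption is arguable. This stands as the better reading. It does not remove the conflict, because no sentence says the note gives way.

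The numerical case is built to straddle the 0.25 limit, and Section 7.1.1.1 labels these priors illustrative, with actual data to replace them. That also stands: the figures show sensitivity to one hypothetical event and not how often the note would apply.

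A reader might infer that the choice of 720/240 mg rests on a miscounted DLT. The documents do not support that. No affected event is described, and Section 1.2.1 reports no event meeting Hy's law in any conducted trial, although that is narrower than an isolated Grade 4 rise.

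Nor would such an event be hidden. Section 5.2.7.1 makes large aminotransferase rises and the combined liver signal a potential-DILI AESI, and under Section 5.2.6.3 the SMC decides on all available safety data.

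A reader might also think that Section 5.2.6.2 needs amending. It does not: once the event counts as a DLT, that section already keeps a patient who discontinues in Cycle 1 because of it.

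Finally, rewording a DLT definition after open-label data have been seen could look like changing the endpoint. That is a fair caution, and it is why any patient whose classification differs should be shown both ways.

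**Conclusion.** The contradiction is real and confined to one line: the AST/ALT criterion against the note in the same cell. For a resolving drug-related Grade 4 rise, the Part 1 primary endpoint and the BLRM input have no single defined value. The proteinuria and combined liver criteria are weakened by the same open-ended note but not contradicted.

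The practical weight is small. Section 4.1.2.2 records that 720/240 mg is selected, and Section 5.2.6.1 ends DLT reporting after Part 1, so no dosing decision is pending. The remaining effect is on the Section 7.3.1.1 DLT counts and BLRM rerun, and only if such an event occurred. This is a minor correction.

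The textual conclusion rests on the protocol alone. The overdose probabilities rest on the illustrative priors and on hypothetical counts.

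**What to change.** State that the note does not apply to the AST/ALT criterion. Preferably, limit it to laboratory abnormalities not listed above it, which also settles the proteinuria and combined liver lines.

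Because Part 1 is complete, check its laboratory events against this wording before the Section 7.3.1.1 summaries and BLRM rerun. Report the counts and the rerun under both readings only if a patient's classification differs, and say so in the report. Leave Section 5.2.6.2 unchanged.

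The cost is one wording change and a check of laboratory events in about 22 Part 1 patients (the synopsis figure). A second BLRM run is needed only if a classification differs.
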